#### 1.4 Pegylated Liposomal Doxorubicin (Doxil® or Lipodox)

Pegylated liposomal doxorubicin (PLD) was first compared with conventional doxorubicin in a randomized, phase III multicenter trial of metastatic breast cancer (MBC). Two hundred ninety-seven patients with MBC and no prior chemotherapy for metastatic disease were randomized to receive either 60 mg/m^2 of PLD or conventional doxorubicin, in combination with 600 mg/m^2 of cyclophosphamide, every 3 weeks until disease progression or unacceptable toxicity. The study showed an improved toxicity panel compared to doxorubicin with significantly reduced cardiotoxicity and less grade 4 neutropenia, while providing comparable antitumor efficacy.[25] This was confirmed in subsequent trials as O'Brien and colleagues compared the use of PLD at a dose of 50 mg/m^2 (every 4 weeks) to doxorubicin 60 mg/m^2 (every 3 weeks). Cardiac event rates were based on reductions in left ventricular ejection fraction as a function of cumulative anthracycline dose. This study demonstrated that in first-line treatment of women with MBC, the efficacy of [progression-free survival (PFS)] of PLD is non-inferior to doxorubicin with significantly less cardiotoxicity, myelosuppression, nausea, and vomiting.[26]

Multicenter randomized phase III trials in multiple myeloma showed that PLD-containing chemotherapy regimens (DVD – PLD (Doxil), vincristine (Oncovin), dexamethasone) compared to a similar doxorubicin-containing regimen (VAD – vincristine (Oncovin), doxorubicin (Adriamycin), dexamethasone) provided similar responses and survival, but that the DVD regimen was associated with significantly less toxicity and supportive care.[27,28] PLD was associated with significantly less grade 3/4 neutropenia or neutropenic fever (10% vs. 24%; p=0.01), less antibiotic use, lower incidence of sepsis, decreased need for central venous access (p<0.0001) and growth factor support (p=0.03) and less alopecia compared to the doxorubicin regimen.[27] A similar decreased toxicity and equivalent tumor response was seen in phase II trials incorporating PLD for doxorubicin in the CHOP regimen for older patients with aggressive (stage III/IV) NHL, in low-grade NHL and in previously untreated aggressive diffuse large B cell lymphoma[28-31]

In a Phase III international study comparing the efficacy and safety of a combination of pegylated liposomal doxorubicin (PLD) plus bortezomib with bortezomib monotherapy in patients with relapsed or refractory multiple myeloma, 646 patients were randomly assigned to receive either intravenous bortezomib 1.3 mg/m^2 on Days 1, 4, 8, and 11 of an every 21-days cycle, or the same bortezomib regimen with PLD 30 mg/m^2 on Day 4. Median time to progression was increased from 6.5 months for bortezomib alone to 9.3 months with the PLD + bortezomib combination (P = 0.000004; hazard ratio, 1.82 [monotherapy v combination therapy]; 95% CI, 1.41 to 2.35). The 15 month survival rate for PLD + bortezomib was 76% compared with 65% for bortezomib alone (P=0.03). The complete plus partial response rate was 41% for bortezomib and 44% for PLD + Bortezomib, a difference that was not statistically significant. Median duration of response was increased from 7 to 10.2 months (P=0.0008) with PLD + bortezomib.

Grade 3 and 4 adverse events were more frequent in the combination group (80% vs. 64%), with safety profiles consistent with the known toxicities of the two agents.

Based on the results of this trial the combination of bortezomib and liposomal doxorubicin (Doxil) received FDA approval for patients who had relapsed/refractory multiple myeloma who had failed at least one line of therapy and had not received prior bortezomib therapy.[17]

In response to a critical shortage of (Doxil), the FDA approved temporary importation of a replacement drug Lipodox (doxorubicin hydrochloride liposome injection) in February 2012. Lipodox has not been approved by the FDA, and therefore, cannot be considered a “generic” of Doxil but has the same active ingredient, dosage, strength, and route of administration. Lipodox is manufactured in a facility that has been inspected by the FDA and found to be in compliance with current good manufacturing practices.

### **1.5 Dexamethasone**

There is increasing data on the superiority of three-drug regimens in the treatment of relapsed and refractory multiple myeloma. Dexamethasone is commonly incorporated in these three-drug regimens because of its ability to improve response rates and duration of response without adding toxicity.

The combination of bortezomib, PLD, and dexamethasone (VDD) has been shown to be efficacious and well tolerated. The overall response and duration of response of VDD exceeds that of the two drug regimens bortezomib-PLD, and bortezomib-dexamethasone suggesting a synergistic effect.[42]

Dexamethasone has been added to carfilzomib, with and without additional agents, in many ongoing clinical trials. These clinical trials have indicated that adding dexamethasone may increase efficacy and tolerability of carfilzomib containing regimens. Many clinical trials that have incorporated dexamethasone into carfilzomib regimens have exceeded the MTD of the single-agent carfilzomib studies.

### **1.6 Rationale**

Based on the further need to improve the therapeutic interventions for multiple myeloma, the previous experience with proteasome inhibition, the potentially improved efficacy of carfilzomib over bortezomib, and the success of bortezomib combination with PLD, the natural next step is to combine carfilzomib with PLD. Furthermore, proteasome inhibitors have the ability to enhance the chemosensitivity in both *in vitro* and *in vivo* preclinical models.[32] Mechanistic studies have indicated that this effect is at least in part due to the inhibition of NF- $\kappa$ B, since many chemotherapeutics activate NF- $\kappa$ B, which can lead to the induction of anti-apoptotic survival proteins such as members of the Bcl-2 family[33]. Several models utilizing anthracyclines in combination with a proteasome inhibitor have shown enhanced anti-tumor activity, including solid tumor models as well as multiple myeloma. Our aim would be to first determine the maximal

tolerated dose of the combination in participants with relapsed/refractory myeloma and then to establish the efficacy of this novel combination[34, 35].

## 1.7 Correlative Studies Background

The correlative studies will focus on two areas:

- (1) evaluation of markers of response
- (2) evaluation of effects of carfilzomib, PLD, and dexamethasone on clonogenic myeloma cells

In order to do so, we will collect bone marrow, peripheral blood, and plasma samples prior to treatment, at time of response, and/or at end of study. The first objective is to determine tumor characteristics that predict at least very good partial response (VGPR). VGPR has been associated with longer progression survival and overall survival. The second objective is to investigate the effects of carfilzomib and PLD on clonogenic myeloma cells. It is hypothesized that inability to cure the disease is related to the inability of eradicating chemoresistant clonogenic myeloma cells or myeloma stem cells. The effect of carfilzomib and its combinations on these cells is not known.

## 2.0 OBJECTIVES

### 2.1 Primary Objectives

- **Phase 1: Part 1-** To determine the Maximal Tolerated Dose (MTD) of carfilzomib in combination with pegylated liposomal doxorubicin (PLD), in participants with relapsed or refractory multiple myeloma. **Part 2-** To determine the Maximal Tolerated Dose (MTD) of carfilzomib in combination with PLD and dexamethasone, in participants with relapsed or refractory multiple myeloma.
- **Phase 2:** To evaluate the efficacy and toxicity of carfilzomib in combination with PLD and dexamethasone in participants with relapsed or refractory multiple myeloma.

### 2.2 Secondary Objectives

- To evaluate the safety of carfilzomib in combination with PLD and dexamethasone in participants with relapsed or refractory multiple myeloma.
- To evaluate the effect of dexamethasone co-administration on the MTD of carfilzomib and PLD
- To evaluate time to tumor progression, progression-free survival, and overall survival in this population treated with carfilzomib in combination with PLD and dexamethasone.

## 3.0 PARTICIPANT SELECTION

### 3.1 Inclusion Criteria

A participant must meet all of the following criteria to be eligible for enrollment.

- 3.1.1** Histologically confirmed diagnosis of multiple myeloma with a measurable disease parameter at time of screening. A measurable disease parameter is defined as one or more of the following:
- Serum monoclonal protein  $\geq 0.5$  g/dl.
  - 24 hour urine monoclonal protein  $\geq 0.2$  g/24 hour
  - Serum free light chain ratio  $> 5x$  normal ratio with an absolute difference of 10mg/dl between the involved and uninvolved free light chain.
  - Soft tissue plasmacytoma  $\geq 2$  cm measurable by either physical examination and/or applicable radiographs (e.g. MRI, CT, etc).
  - Bone Marrow Plasma Cells  $\geq 30\%$ .
- 3.1.2** Documentation of at least one line of prior myeloma therapy now with relapsed or refractory disease requiring re-treatment.
- 3.1.3**  $\geq 18$  years of age at time of signing the informed consent.

*Note:* No dosing or adverse event data are currently available on the use of carfilzomib in combination with PLD in participants  $< 18$  years of age. Thus, children and adolescents are excluded from this study but will be eligible for future pediatric phase 2 combination trials.

- 3.1.4** Performance status of ECOG  $\leq 2$  or Karnofsky  $\geq 60$  % (see Appendix A and B).

*Note:* Participants with lower performance status based solely on bone pain secondary to multiple myeloma will be eligible.

- 3.1.5** Required Laboratory Values
- ALT (SGPT) and AST (SGOT)  $< 2.5$  x the upper limit of the institutional normal value (ULN).
  - Total bilirubin  $\leq 1.5$  x ULN.
  - ANC  $\geq 1,000$ .
  - Hemoglobin  $\geq 8$  g/dl.
  - Platelets  $\geq 50,000$ .
  - Creatinine clearance  $> 15$  ml/minute using Cockcroft-Gault formula (See Appendix C).
  - For those participants receiving warfarin (Coumadin), unfractionated heparin, or low-molecular weight heparin therapy, the applicable

coagulation parameter that is being monitored must be within the accepted therapeutic ranges for those indications.

*Note:* Transfusions and/or growth factor dependent participants are not excluded if the above parameters can be achieved with such support.

- 3.1.6** Females of childbearing potential (FCBP) must agree to refrain from becoming pregnant while on study drug and for 3 months after discontinuation from study drug, and must agree to use adequate contraception including hormonal contraception, (i.e. birth control pills, etc), barrier method contraception (i.e. condoms), or abstinence during that time frame.

FCBP must agree to regular pregnancy testing during this timeframe (see section 10.1). Inclusion of FCBP requires two negative pregnancy tests prior to enrollment.

*Note:* all women, regardless of age, should be considered FCBP unless they are surgically sterile (post hysterectomy, post bilateral oophorectomy, etc) or have been naturally post menopausal for  $\geq 24$  consecutive months.

- 3.1.7** Men engaging in sexual intercourse with a FCBP must agree to use adequate contraception including hormonal contraception, (i.e. birth control pills, etc), barrier method contraception (i.e. condoms), or abstinence while on study drug and for 3 months after discontinuation from study drug

- 3.1.8** Ability to understand and willing to sign a written informed consent document.

## **3.2 Exclusion Criteria**

A participant must not meet any of the following criteria to be eligible for enrollment.

- 3.2.1** POEMS syndrome (polyneuropathy, organomegaly, endocrinopathy, monoclonal protein, and skin changes).
- 3.2.2** Plasma Cell Leukemia.
- 3.2.3** Waldenstrom's macroglobulinemia.
- 3.2.4** Pregnant or lactating females.
- 3.2.5** Use of any anti-myeloma drug therapy within 14 days of initiation of study drug treatment excluding corticosteroids if given for an indication other than myeloma.

*Note:* Bisphosphonates are not considered anti-myeloma drugs.

- 3.2.6** Participation in an investigational therapeutic study within 14 days of initiation of study drug treatment.
- 3.2.7** Radiotherapy to multiple sites or immunotherapy within 14 days of initiation of study drug treatment (localized radiotherapy to a single site at least 7 days before start is permissible).
- 3.2.8** Major surgery within 14 days of initiation of study drug treatment.
- 3.2.9** Participants in whom the required program of PO and IV fluid hydration is contraindicated.
- 3.2.10** Prior history of a hypersensitivity reaction to PLD, doxorubicin, bortezomib, carfilzomib, or liposomal drug formulations other than PLD.

History of reactions to liposomal drug formulations other than PLD should be evaluated individually and if their reactions were felt to have been due to the encapsulated agent, rather than the liposomal component itself they should be excluded at the discretion of the investigators.

- 3.2.11** Participants who are known to have active hepatitis A, B, or C viral infection may not participate in this study. Active disease is defined as participants with a known viral hepatitis whose liver function tests are elevated beyond the criteria indicated in Section 3.1.5.
- 3.2.12** Known HIV-seropositive and are taking anti-retrovirals may not participate in this study because of potential interactions between these medications and the investigational agent. Participants who are HIV-seropositive and not on anti-retroviral therapy and who otherwise meet the inclusion/exclusion criteria will be eligible for the study.
- 3.2.13** Compromised cardiovascular function defined as any of the following:
  - EKG evidence of acute ischemia.
  - EKG evidence of medically significant conduction system abnormalities.
  - History of myocardial infarction within the last 6 months.
  - Unstable angina pectoris or cardiac arrhythmia.
  - History of Class 3 or Class 4 New York Heart Association Congestive Heart Failure
  - Left ventricular ejection fraction (LVEF) < 55% by either echocardiography or radionuclide-based multiple gated acquisition (Echo or MUGA).

**3.2.14** Uncontrolled concurrent illness including: other hematologic or non-hematologic malignancy, active infection, or uncontrolled diabetes

**3.2.15** Any significant psychological, medical, or surgical condition thought to compromise the participant, the study, or prevent informed consent.

### **3.3 Inclusion of Women and Minorities**

Both men and women and members of all races and ethnic groups are eligible for this trial.

## **4.0 REGISTRATION PROCEDURES**

**Patients must not start any protocol intervention prior to registration through the Siteman Cancer Center.**

The following steps must be taken before registering patients to this study:

1. Confirmation of patient eligibility
2. Registration of patient in the Siteman Cancer Center database
3. Assignment of unique patient number (UPN)

### **4.1 Confirmation of Patient Eligibility**

Confirm patient eligibility by collecting the information listed below:

1. Registering MD's name
2. Patient's race, sex, and DOB
3. Three letters (or two letters and a dash) for the patient's initials
4. Copy of signed consent form
5. Completed eligibility checklist, signed and dated by a member of the study team
6. Copy of appropriate source documentation confirming patient eligibility

### **4.2 Patient Registration in the Siteman Cancer Center Database**

All patients must be registered through the Siteman Cancer Center database.

### **4.3 Assignment of UPN**

Each patient will be identified with a unique patient number (UPN) for this study. Patients will also be identified by first, middle, and last initials. If the patient has no middle initial, a dash will be used on the case report forms (CRFs). All data will be recorded with this identification number on the appropriate CRFs.

## 5.0 TREATMENT PLAN

### 5.1 Overview

Carfilzomib will be administered on Days 1, 2, 8, 9, 15, and 16 during Cycles 1 through 6, and on Days 1, 8, 15, and 22 beginning on Cycle 7 until disease progression or clinical relapse. Participants treated prior to approval of amendment 1, will have carfilzomib administered on Days 1, 2, 8, 9, 15, and 16 during Cycles 1 and 2 and on Days 1, 8, 15, and 22 beginning on Cycle 3. PLD will be administered on Day 8 during Cycles 1 through 6. Dexamethasone will be administered on the same schedule as carfilzomib (patients treated in part 2 of phase 1 or phase 2).

Participants that have PLD or dexamethasone discontinued for toxicity may remain on study to receive the planned study drug doses at the PI's discretion.

### 5.2 Phase I

Part 1- A phase I dose escalation of carfilzomib and PLD will be performed using a standard 3 + 3 design with a maximum of 4 dose levels (24 participants). The carfilzomib dose will be determined using a modified Fibonacci dose escalation, with a goal of three participants at each dose level.

Dose Level	Carfilzomib (mg/m  ) IV	PLD (mg/m  ) IV
-2	20	20
-1	20 on D1 and D2* 27 starting on D8	20
0 (Start)	20 on D1 and D2* 27 starting on D8	30
1	20 on D1 and D2* 36 starting on D8	30
2	20 on D1 and D2* 45 starting on D8	30
3	20 on D1 and D2* 56 starting on D8	30

\*- Please note that the D1 and D2 carfilzomib dose of 20mg/m^2 will only occur during Cycle 1. For all subsequent cycles, patients will receive the same dose of carfilzomib throughout at what is noted in this table to be the D8 dose.

Part 2- After the MTD of carfilzomib in combination with PLD has been determined, dose escalation will resume at the MTD of carfilzomib and PLD with the addition of dexamethasone. A maximum of 12 participants eligible for Maximal Tolerated Dose (MTD) analysis will be enrolled.

Dose Level	Carfilzomib (mg/m  ) IV	PLD (mg/m  ) IV	Dex (mg) IV or PO
-1	1 dose level below the MTD	1 dose level below the MTD	20
0 (Start)	MTD	MTD	20

### 5.2.1 Dose Escalation Rule

Number of Participants with a DLT at a Dose Level	Escalation Decision Rule
0	Enter 3 participants at the next dose level.
1 out of 3	Enter 3 more participants at this dose level.  If none of the additional participants experiences a DLT, then proceed to the next dose level. If $\geq 1$ of the additional participants experiences a DLT, then dose escalation is stopped and the level below is declared the MTD.
$\geq 2$	Dose escalation is stopped. Enter 3 more participants at the next lower dose level if only 3 participants had previously been treated at that dose level.

Only after the last participant on at each dose level completes one cycle of treatment will the first participant in the next dose level be enrolled.

### 5.2.2 Definition of Maximum Tolerated Dose

The maximum tolerated dose (MTD) is defined as the dose level immediately below the dose level at which 2 participants of a cohort (of 2 to 6 participants) experience dose limiting toxicity (DLT) during the first cycle of treatment. (See Section 6.0 for information on what constitutes a DLT.) Dose escalation will proceed until the MTD has been reached.

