## 5.3 Phase II

Having established an MTD in phase I, phase II will be conducted to assess the efficacy and toxicity of carfilzomib in combination with PLD and dexamethasone in participants with relapsed or refractory multiple myeloma.

Seventeen participants will be treated at the MTD of carfilzomib in combination with PLD and dexamethasone. Participants treated in phase 1 at the MTD will be counted as part of the phase two accrual. If  $\leq 5$  successes (CR, VGPR, or PR) are observed, we will

consider this regimen ineffective in this participant population and will not recommend further testing.

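### In Part 2, if the start level fails, the rules name three-drug level -1 as the MTD although nobody has been treated there

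*Combined protocol and SAP*

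**What the plan says.** Section 2.1 makes the three-drug dose a primary objective: "To determine the Maximal Tolerated Dose (MTD) of carfilzomib in combination with PLD and dexamethasone". For Part 2, section 5.2 says that "dose escalation will resume at the MTD of carfilzomib and PLD with the addition of dexamethasone". The Part 2 table lists two levels, both with dexamethasone 20 mg: level 0 (start) at the two-drug MTD, and level -1 one dose level below it. On numbers: "A maximum of 12 participants eligible for Maximal Tolerated Dose (MTD) analysis will be enrolled".

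The table in 5.2.1 has two rows that stop escalation.

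- Second row: 1 of 3 has a DLT, 3 more are entered, and at least 1 of those has a DLT; "then dose escalation is stopped and the level below is declared the MTD".
- Third row: 2 or more have a DLT. Escalation stops, with the instruction "Enter 3 more participants at the next lower dose level if only 3 participants had previously been treated at that dose level".

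Section 5.2.2 says that the MTD "is defined as the dose level immediately below the dose level at which 2 participants of a cohort" have a cycle 1 DLT. It sets neither a minimum number treated nor a maximum DLT count at the level so named.

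Section 5.3 then states "Seventeen participants will be treated at the MTD of carfilzomib in combination with PLD and dexamethasone" and "Participants treated in phase 1 at the MTD will be counted as part of the phase two accrual".

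**The concern.** The 5.2.1 rules suit a climb from below, where the level beneath a failing one has already been treated. Part 2 begins at the top of its two levels. When level 0 fails, three-drug level -1 has no participants, yet the rules still point to it.

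On that path the Part 2 primary objective is answered without data from the level named. Nobody from phase I was treated at the MTD, so all 17 phase II participants in 5.3 would be new. No group-level tolerability decision comes first: 5.3 and 16.0 contain only response counts. Section 6.2.1 makes the stated dose modifications binding in cycle 1 of phase I but lets the Principal Investigator vary them in any phase II cycle.

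Part 1 data fill the gap only in part. If the Part 1 MTD is level 1 or higher, the carfilzomib and PLD doses one row down were cleared in Part 1, but with 4 mg dexamethasone premedication in cycle 1 (7.1.4). Dexamethasone 20 mg could be added only after cycle 2 (7.3.4), outside the DLT window. If the Part 1 MTD is level 0 or lower, no phase I cohort received the doses one row down.

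**Working it through.** **The plan's own figures.** At 6 participants per level, Part 2 needs 2 x 6 = 12 and Part 1 needs 4 x 6 = 24. Both match the caps in 5.2. The Part 2 cap therefore has room for a full cohort at level -1.

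**Tracing the rules when Part 2 level 0 fails.** Participants already treated at three-drug level -1: 0.

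| Failure route | 5.2.1 at level -1 | MTD under 5.2.2 |
|---|---|---|
| 1 of 3, then at least 1 of 3 more | declared the MTD; no enrolment step | level -1 |
| 2 or more of 3 | 3 more only if 3 already treated; condition not met | level -1 |

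**How often level 0 fails.** The documents give no DLT rates, so p, the true cycle 1 DLT rate at level 0, is assumed. With q = 1 - p:

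- third-row failure = 3p²q + p³
- second-row failure = 3pq² x (1 - q³)

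At p = 0.20: third row = 3(0.04)(0.8) + 0.008 = 0.104; second row = 3(0.2)(0.64)(1 - 0.512) = 0.187; total 0.291.

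| p at level 0 | second row | third row | level 0 fails |
|---|---|---|---|
| 10% | 6.6% | 2.8% | 9.4% |
| 20% | 18.7% | 10.4% | 29.1% |
| 30% | 29.0% | 21.6% | 50.6% |
| 40% | 33.9% | 35.2% | 69.1% |

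**What a check of 6 at level -1 would do.** With p now the true rate at level -1, P(2 or more DLTs in 6) = 1 - q⁶ - 6pq⁵. This gives 11.4% at p = 10%, 34.5% at 20% and 58.0% at 30%.

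**How often level -1 would be too toxic.** This needs an assumed dose-toxicity curve, followed through Part 1 by exact enumeration. A level with 0/3 or 1/6 escalates. A second-row stop names the level below. A third-row stop takes the level below to 6 if 3 were treated there, and moves down again at 2 or more of 6. A cleared level 3 is carried forward. Assumed two-drug DLT rates at levels -2 to 3:

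- low: 2, 3, 5, 10, 15, 20%
- middle: 5, 7, 10, 20, 30, 40%
- high: 10, 15, 20, 30, 40, 50%

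The Part 2 rate is the two-drug rate times a dexamethasone factor of 0.75, 1.0 or 1.25, which makes nine settings. Part 2 level -1 is read as one row down in the Part 1 table.

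Middle curve: the Part 1 MTD falls at levels -1, 0, 1, 2, 3 with probability 0.096, 0.273, 0.330, 0.203, 0.098. At factor 1.0, P(start fails) = 0.096 x 0.050 + 0.273 x 0.094 + 0.330 x 0.291 + 0.203 x 0.506 + 0.098 x 0.691 = 0.297.

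| Curve | start fails, factor 0.75 / 1.0 / 1.25 | start fails and true rate at level -1 above one-third |
|---|---|---|
| low | 12.9 / 20.5 / 28.5% | 0 / 0 / 0% |
| middle | 19.9 / 29.7 / 38.9% | 0 / 0 / 8.1% |
| high | 23.5 / 35.0 / 46.0% | 0 / 1.5 / 8.1% |

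The one-third benchmark is also an assumption. The three non-zero entries, using P(fail) = 0.828 at a 50% rate and 0.933 at 62.5%, are:

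- middle, 1.25: Part 1 MTD at level 3 (0.098), start rate 50%, one row down 37.5%: 0.098 x 0.828 = 0.081
- high, 1.0: Part 1 MTD at level 3 (0.0186), start rate 50%, one row down 40%: 0.0186 x 0.828 = 0.015
- high, 1.25: Part 1 MTD at level 3 (0.0186, start rate 62.5%) or level 2 (0.0764, start rate 50%): 0.0186 x 0.933 + 0.0764 x 0.828 = 0.081

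**The case against.** The best defence is intent. Section 5.2 invokes a standard 3 + 3 design (in the Part 1 sentence). The Part 2 table lists level -1, and the cap of 12 is twice what the start level can use. Section 5.3 also expects phase I participants at the MTD. An investigator would probably treat a cohort at level -1. The third row can be read as silent about an untreated level rather than as an instruction to skip it. All of this is fair, and it makes the gap look like a drafting omission. But a cap is a ceiling, and none of these sentences overrides the second row, which declares the MTD with no enrolment step.

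A second defence is that level -1 is lower than the dose that failed. Section 1.5 expects dexamethasone to add no toxicity and possibly to improve tolerability, so a factor of 1 or less is the documents' own view. If the Part 1 MTD is level 0, one row down keeps the same carfilzomib and lowers PLD from 30 to 20 mg/m², so clearance of level 0 is informative. These points stand, and they limit the likely harm.

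Three stronger readings are tempting and are not supported.

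- A reader might take 9 to 69% as the chance of opening phase II at a toxic dose. It is only the chance that the start level fails.
- A reader might use the chance that the start fails and level -1 would then show 2 or more DLTs in 6, which is 1.5 to 19.2% over the nine settings. Much of that is chance rejection of acceptable doses. On the middle curve at factor 1.0, 4.8 of the 8.7 percentage points come from true rates of 20% or less.
- A reader might infer that phase II is unprotected. It keeps pre-dose laboratory checks, toxicity-specific holds and reductions, expedited reporting, ongoing serious-toxicity monitoring and semi-annual committee reports. What it lacks is a group-level tolerability gate.

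**Conclusion.** The concern holds for Part 2. If the start level fails by the second row, the text names an untreated three-drug level as the MTD. If it fails by the third row, no cohort there is required and 5.2.2 names the same level. The result follows from the rules as written.

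It does not extend to Part 1 in the same way: a level named there, even if untreated, is tested with dexamethasone 20 mg as the Part 2 start level before phase II.

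The path is not remote: 9.4 to 69.1% at assumed start-level DLT rates of 10 to 40%, of which the explicit second-row route contributes 6.6 to 33.9 percentage points. The chance that it leads to a level with a true DLT rate above one-third is much smaller: zero in six of the nine scenarios and at most about 8%, and both settings near 8% need dexamethasone to raise DLT rates by 25%. All rates are assumed. The point should be fixed because a primary objective depends on it and the repair is cheap, not because a toxic phase II dose is likely.

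**What to change.** Add to 5.2.1 and 5.2.2, for Part 2 only:

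- If level 0 fails by either stop row, treat 3 and then 3 more DLT-evaluable participants at level -1 under the 6.1 definitions, stopping at a second DLT.
- Declare level -1 the MTD only when all 6 have been evaluated and no more than 1 has had a DLT.
- If 2 or more have DLTs, do not open phase II without a protocol amendment naming a lower dose. Part 2 lists nothing below level -1.

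Six matches the third row, which already takes a treated lower level from 3 to 6. The rule for clearing the start level does not change.

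Cost: two or three sentences, and up to 6 participants, only if the start level fails. 6 + 6 = 12 is the existing cap, and the 6 count towards the 17 if level -1 passes. At the 5.5 rates, 6 participants take 6 months at 1 a month, against 3 to 6 months at 1 to 2 a month. That adds 0 to 3 months, plus one 28-day cycle for the last participant: about 1 to 4 months. The largest cost is that an acceptable level -1 may be rejected, with probability 11.4% at a true DLT rate of 10% and 34.5% at 20%; phase II would then wait for an amendment.
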